[1] Theory driven based on prior knowledge: A list of recognised prognostic factors for abnormal monitoring blood test results have been developed based on the research teams' clinical experience. The a priori agreed prognostic factors include: age, sex, body mass index, alcohol consumption, smoking, CKD stage 3, type 2 diabetes, and prescription of selected drugs that increase risk of acute kidney injury or transaminase elevation at baseline.

[2] Evidence based, based on systematic review: A systematic review of existing literature is currently underway to identify other prognostic factors. This will provide additional candidate predictors (PROSPERO: CRD42020208049).

The presence of comorbid and lifestyle prognostic factors will be ascertained using primarycare diagnoses and lifestyle data collected in the two-years preceding cohort entry. The presence of prescription prognostic factors will be ascertained using primary-care prescriptions in the 180 days preceding cohort entry.

Outcomes

Primary outcome: Target organ specific adverse event resulting in drug discontinuation from 6 months of initial primary-care prescription to until 5-years after the initial prescription.

This will be defined as drug discontinuation with either (a) diagnosed with target organ damage based on clinical code, or (b) significant abnormal blood test results.

Drug discontinuation due to abnormal monitoring blood test results will be defined as present when there is:

(a) a gap between two prescriptions, or between last prescription date and earliest of death date, moving to a different practice, 5-year follow-up time, or 31/12/2019 (study end date) of \geq 90 days, and

(b) an abnormal blood-test result in the 15 days preceding or 45 days after the last prescription date. The 15-day preceding window is to allow for any delay in acting on abnormal blood-test results.

Abnormal blood test results will be defined according to the British Society for Rheumatology DMARD monitoring guidelines 1, and CKD progression will be defined as per the Kidney Disease Improving Global Outcomes guideline 20122:

- White blood cells <3.5x109/L,
- Neutrophils <1.6x109/L,
- Platelets <140x109/L,
- Alanine Transaminase and/or Aspartate Transaminase >100 units/L,

• CKD progression defined as creatinine difference > 26 micro mol/L above the first or second preceding result or chronic kidney disease stage progression.

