In addition, in people with psoriasis (but without arthritis), methotrexate discontinuation will be defined to be due to blood-test abnormalities if (i) serum amino-terminal propeptide of type III procollagen (PIIINP) is > 8 mg/L on two previous occasions; (ii) if three previous PIIINP measurements were >4.2 mg/L in the previous 12-month period; or (iii) if previous PIIINP measurement was > 10 mg/L as per guidelines for the the British Association of Dermatologists [3].

Primary outcome identification: Study participants who have the outcome of interest will be identified as follows:

Step 1: All participants with drug discontinuation as defined above will be identified.

Step 2: The results of their blood tests from up to 15 days before and 45 days after the last DMARD prescription date, and the dates of blood tests will be extracted.

Step 3: All other Read code entries in the clinical and investigation files indicating abnormal blood test results within this 60-day period (-15 to + 45 days), and the date of such entry will be extracted.

Step 4: Participants with abnormal blood test results or a Read code specifying abnormal blood test results within this period and their date of event will be ascertained.

Secondary outcome: Drug discontinuation due to any reason. Defined as a gap between two prescriptions, or between last prescription date and earliest of death date, moving to a different practice, 5-year follow-up time, or 31/12/2019 (study end date) of \geq 90 days. Data/statistical analysis

Mean (standard deviation), and n (%) will be used for descriptive purposes.

Derivation and validation of the risk prediction model:

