for other clinical events, the occurrence of abnormal blood tests is recorded using Read codes such as R144.11 (kidney function test abnormal), KO4..12 to KOE.0 (acute kidney injury) etc.; R148.00 and 44D2.00, 44G2.00 etc. (liver function test abnormal or abnormal liver enzymes); and D400.12 and 42J2.00 etc. (neutropenia) and D400600 and D400211 etc. (drug induced neutropenia); D315.00 D313z00 and 42P2.00 (thrombocytopenia). To reduce the risk of missing data, we will use either numerical blood test results or Read codes to define the outcome of interest. To minimise the risk of bias from missing data, participants with only one full blood count, liver function test and renal function test in the first year of drug prescription in primary care will be excluded from analysis. Similar steps will be taken in CPRD Aurum where applicable. For example, cleansedreadcode which define the occurrence of abnormal blood tests such as 44J3000 (serum creatinine abnormal), KO4..00 (acute renal failure); R148.11 (LFT's abnormal) and 44D2.00 (liver function test abnormal); and 42J2.00 (Neutropenia), 42J4.00 (Neutrophil count abnormal); 42H2.11 (Leucopenia) and 42P2.00 (thrombocytopenia) will be used in instances of missing numerical blood test results in Aurum.

Patient or user group involvement

The PPI panel will review and feedback on the performance of risk scores, with information presented in a way that is accessible to lay members. The risk prediction calculation will be applied to hypothetical case scenarios and the results presented to the PPI members to gauge initial acceptability. They will also comment on the net risk and net benefit from different monitoring strategies compared to no testing or testing all. Plans for disseminating and communicating study results

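### Unspecific Read codes can stand in for the numeric limits of the primary outcome, and the protocol does not say, consistently for Gold and Aurum, whether a recorded value below the limit overrides them

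*Protocol*

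**What the plan says.** Under *Outcomes*, the Protocol defines an abnormal result by numeric limits with a direction: white cells below 3.5, neutrophils below 1.6 and platelets below 140 (all x10^9/L), "Alanine Transaminase and/or Aspartate Transaminase >100 units/L", and a creatinine rise of more than 26 micromol/L or a step up in kidney disease stage. A separate limb of the primary outcome accepts target-organ damage recorded by clinical code.

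Under *Primary outcome identification*, discontinuation comes first: "Step 1: All participants with drug discontinuation as defined above will be identified". Numeric results are then extracted, and so are Read codes for abnormal tests "within this 60-day period (-15 to + 45 days), and the date of such entry will be extracted". Step 4 counts "Participants with abnormal blood test results or a Read code specifying abnormal blood test results within this period". No database is named.

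Under *Plans for addressing missing data*, in the paragraph on missing blood test results, the protocol says "we will use either numerical blood test results or Read codes to define the outcome of interest". The codes listed before that sentence include entries for abnormal kidney function and abnormal liver function tests, alongside entries for acute kidney injury, neutropenia and thrombocytopenia. It continues "Similar steps will be taken in CPRD Aurum where applicable". It then gives Aurum examples, including abnormal liver function, abnormal serum creatinine and "42J4.00 (Neutrophil count abnormal"), and says that these "will be used in instances of missing numerical blood test results in Aurum".

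**The concern.** Codes for an abnormal liver function test, kidney function test or serum creatinine record that something was out of range. They do not say by how much. The neutrophil entry does not say in which direction. If such a code may replace the numeric criterion even when the number is on file, the endpoint admits patients whose own recorded value shows that the limit was not met. *Study background* notes that older studies stopped treatment at ALT of 1.2 to 1.4 times the upper limit of normal, well below the current threshold. Unspecific codes could bring abnormalities of that size back into an outcome labelled target-organ damage.

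The second issue is the wording by database. The Aurum sentence makes the code a fallback, whereas the general sentence and Step 4 make it an alternative. Four models are developed in Aurum and validated in Gold, and methotrexate runs the other way. A difference in event definition between the databases would appear as miscalibration. Predicted risks then feed the decision curves and the choice of risk thresholds.

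**Working it through.** **1. One patient under each rule.** Take a patient with a prescription gap of at least 90 days, an ALT of 55 units/L within -15 to +45 days of the last prescription, and code 44D2.00 (abnormal liver function test) in the same window. This code appears in both the general and the Aurum lists.

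| Rule | Event? |
|---|---|
| Numeric limit in *Outcomes* (above 100) | No |
| Steps 3-4, result or code | Yes |
| General sentence in the missing-data section, either/or | Yes |
| Aurum sentence, code only if the number is missing | No |

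Nothing states which source prevails when both are present.

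**2. Would a planned check reveal such events?**
- The review of 505 sampled methotrexate cases (*Feasibility counts*) asked whether another illness could explain the discontinuation. It did not ask whether the limit was met.
- The HES exercise (*Planned use of linked data*) estimates sensitivity only. Its reference standard is the outcome from primary care plus HES, so a false-positive primary-care event counts as a true one.

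Neither would detect the problem.

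**3. The protocol's own figures.** Events 1,262 and users 15,670 come from *Feasibility counts*.
- Proportion: 1,262 / 15,670 = 8.05%, which agrees with the stated 8%.
- 99% margin: 2.576 x sqrt(0.08 x 0.92 / 15,670) = 0.558%, against 0.55% stated. This agrees to rounding.

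No stated figure is wrong on this point.

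**4. Possible size.** Let f be the share of either/or events that rest only on an unspecific code while a recorded value is inside the limits. The documents do not give f, so the values below are assumptions. The table also assumes that the 1,262 were counted under the either/or rule (the protocol does not say so), that the Aurum sentence is applied literally, and that the model is otherwise perfectly calibrated.

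- Events left under the missing-only rule = 1,262 x (1 - f)
- Observed/expected, developed either/or and validated missing-only (methotrexate, Gold to Aurum) = 1 - f
- Observed/expected in reverse (other drugs, Aurum to Gold) = 1 / (1 - f)

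| f (assumed) | Events | Proportion | O/E, methotrexate | O/E, other drugs |
|---|---|---|---|---|
| 0 | 1,262 | 8.05% | 1.00 | 1.00 |
| 5% | 1,199 | 7.65% | 0.95 | 1.05 |
| 10% | 1,136 | 7.25% | 0.90 | 1.11 |
| 20% | 1,010 | 6.44% | 0.80 | 1.25 |

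The last column applies the methotrexate-based f to other drugs and is illustrative only.

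**The case against.** The strongest reply is that the protocol intends a single procedure. The either/or sentence sits in a paragraph about numeric results that are not available, and its stated purpose is to reduce missing data. The Aurum text is introduced as similar steps and offered as an example. Steps 1 to 4 name no database, and *Derivation and validation of the risk prediction model* promises the same code search strategy for both. This stands as far as intent goes. A reader might infer that the protocol fixes two different endpoints and that external validation must compare them. The documents do not support that: they show a wording conflict left unreconciled. A shared search strategy does not resolve it, however, because it harmonises the code list and not the precedence between code and number.

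Three other stronger readings also fail.
- A reader might infer that a code makes an event by itself. It does not: the 90-day gap and the -15 to +45 day window are also required.
- A reader might cite a recorded high neutrophil count plus the unspecific neutrophil code as a certain false event. That code is listed only for Aurum, where the missing-only sentence would block it. The example works only if the either/or wording of Step 4 governs Aurum too, and in that case the difference between databases disappears. Under the Aurum sentence the remaining risk is a high count with no number on file.
- A reader might treat misclassification as established and attach a figure to it. Nothing in the documents gives the code-only share. Adding assumed false events on top of the 1,262 could also double-count, since they may already be included.

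It is also fair that the lists are illustrative and that several entries state a diagnosis or a direction. Final code lists can come later. Precedence between a code and a contrary value is different: the protocol already states it, in two incompatible ways, for the primary outcome. The *Limitations* section prefers over-counting to under-counting, but says so only for unrecorded biologics. It does not address over-counting that could differ between the development and validation databases.

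**Conclusion.** The point holds as a conflict in the outcome definition. Step 4 and the general missing-data sentence let an unspecific code replace the numeric limits even when a recorded value shows that the limit was not met. The Aurum sentence does not. Events can be misclassified, and apparent miscalibration at external validation can partly reflect the definition. Neither outcome check described in the protocol would reveal this.

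The size is unknown. The observed/expected range of 0.80 to 1.25 follows entirely from assuming f between 5% and 20% and from applying the two wordings literally, one in each database. If no events rest on an unspecific code with a contrary value, or if one rule is in fact applied to both databases, the effect on validation is nil. In the second case the choice of rule still determines who counts as an event. It is worth settling before extraction, but it does not undermine the design.

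**What to change.** State one rule for both databases under *Primary outcome identification* (Steps 3-4) and repeat it in the missing-data section:

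- An unspecific abnormal-test code counts only when no numeric result for that analyte is recorded from day -15 to day +45 around the last prescription. Where one is recorded, the limit in *Outcomes* decides.
- Codes that state a diagnosis or a direction (neutropenia, leucopenia, thrombocytopenia, acute kidney injury) continue to count under the clinical-code limb of the primary outcome. This carve-out is needed: letting the number decide in every case would cancel a coded diagnosis whenever one value inside the limits falls in the window, for example after recovery, and would contradict that limb.
- The neutrophil code without direction no longer qualifies on its own.
- Report, by database and drug, the share of events that rest on a code alone.
- Add a sensitivity analysis that excludes events resting only on unspecific codes.

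The cost is a few sentences, a small change to the extraction logic and one further analysis. The downside is a somewhat smaller event count. For methotrexate even the 20% illustration leaves 1,010 events, against the 329 that the protocol's sample-size calculation requires. For less often prescribed drugs the loss cannot be judged from the documents.

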(a) a gap between two prescriptions, or between the last prescription date and earliest of death date, moving to a different practice, 5-year follow-up time, or 31/12/2019 (study end date) of \geq 90 days, and

(b) the last prescription is preceded in up to 15 days by abnormal blood test results (to account for any delay in acting on abnormal results) or followed by an abnormal test result in the next 45 days.

Abnormal blood test results will be defined according to the British Society for Rheumatology DMARD monitoring guidelines1, and CKD progression will be defined as per the Kidney Disease Improving Global Outcomes guideline 20122:

- White blood cells <3.5x109/L,
- Neutrophils <1.6x109/L,
- Platelets <140x109/L,
- Alanine Transaminase and/or Aspartate Transaminase >100 units/L,

• CKD progression defined as creatinine difference > 26 micro mol/L above the first or second preceding blood-test result or chronic kidney disease stage progression.

In addition to the above blood-test abnormalities, in people with psoriasis, methotrexate discontinuation will be defined to be due to blood-test abnormalities if (i) serum amino-terminal pro-peptide of type III procollagen (PIIINP) is > 8 mg/L on two previous occasions; (ii) if three previous PIIINP measurements were >4.2 mg/L in the previous 12-month period; or (iii) if previous PIIINP measurement was > 10 mg/L as per guidelines for the British Association of Dermatologists [3].

Secondary outcome: Drug discontinuation due to any reason.

Defined as present if there is a gap between two prescriptions, or between last prescription date and earliest of death date, moving to a different practice, 5-year follow-up time, or 31/12/2019 (study end date) of ≥ 90 days.

Objectives, specific aims and rationale

The overall purpose of this study is to ascertain the optimum strategy of blood testing for adults with common inflammatory conditions treated with immune-suppressing drugs after the first six months of primary-care prescription. By strategy we mean the optimum frequency of testing, and how the frequency of testing should alter according to the individual's risk.

The objectives are to:

[1] Develop and validate a prediction model estimating an individual's risk of target-organ damage conditional on their values of multiple prognostic factors available at six months of immune-suppressing drug prescription.

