Cohort entry and start of follow-up: At first prescription and day 180 of the first primarycare prescription of a drug of interest respectively. Separate cohorts will be built for each drug.

Cohort exit: Earliest of target-organ adverse event, drug discontinuation, death, moving to a different practice, 5-year follow-up time, or 31/12/2019 (study end date).

Inclusion criteria:

[1] Diagnosis of any common inflammatory disease i.e. RA, inflammatory bowel disease, psoriasis +/- arthritis, ankylosing spondylitis, systemic lupus erythematosus, or reactive arthritis. These are the commonest inflammatory conditions treated with immune-suppressive drugs.

[2] Age ≥18 years at diagnosis.

[3] At least one GP prescription of methotrexate, azathioprine (or mercaptopurine), aminosalicylates, sulfasalazine, mycophenolate. These are the most commonly prescribed immune-suppressing drugs for which blood test monitoring is recommended.
[4] Meeting CPRD data quality standards (UTS for Gold and acceptable flag for Aurum) and with a continuous registration for at least one year before the first date of diagnosis of inflammatory disease in CPRD Gold and CPRD Aurum.

The requirement to have one-year disease free registration in the CPRD prior to first date of inflammatory disease diagnosis is to allow for the identification of incident cases, and those newly commenced on immune-suppressing drugs. This will exclude prevalent cases of inflammatory diseases on long-term hospital prescribed immune-suppressive drugs who have recently switched to GP prescription due to implementation of primary-care/secondary-care shared care prescribing in their area.

Exclusion criteria: Presence of any of the below prior to cohort entry:

[1] eGFR < 15 ml/min or chronic kidney disease stage 4 or 5.

[2] Chronic liver disease: Autoimmune hepatitis, hepatitis B or C, cirrhosis

[3] Pre-existing hematological abnormalities: Myelodysplasia, primary hematological diseases causing neutropenia or thrombocytopenia.

[4] Prescription of the immunosuppressive drugs listed above before first inflammatory disease diagnosis date.

[5] Registered in GP practices not meeting CPRD data quality standard at cohort entry.

Selection of comparison group(s) or controls

A comparison group is not applicable in the context of risk prediction modelling. Exposures, outcomes and covariates

Predictors of drug discontinuation: Candidate prognostic factors will be identified using two approaches:

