Incidence of drug discontinuation: Survival analysis will be undertaken to calculate the incidence rate of drug discontinuation (95% confidence intervals (CI)) per 1,000 personyears for entire study period, first 12-months of follow-up, and the subsequent period. Life tables will be constructed to estimate the cumulative incidence at 1-year and 5-year follow-up. Cumulative hazards will be plotted using Nelson-Aalen graphs. Data management and analysis will be performed in Stata MP v16.

Plan for addressing confounding

Bias due to transferring GP surgeries: To minimise bias due to prevalent users appearing as incident users in a new GP surgery, data for participants who receive a prescription of a DMARD within one year of their current registration in a GP surgery will be excluded from the cohort. This will minimise the chance of prevalent long-term users of these medicines entering the cohort as new incident-users.

Plans for addressing missing data

Multiple imputation using chained equations will be used to deal with missing data. We expect BMI, alcohol intake, smoking and ethnicity to have missing values. The number of imputations will depend on the extent of the missing data.

Missing data on blood test results: The CPRD has data about blood test results. However, it is possible that in some instances of drug discontinuation due to abnormal monitoring blood test results, the numerical blood test results are not available in the CPRD. However, just as

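### The blood-test completeness exclusion counts tests over the whole first year although follow-up starts at day 180, so inclusion depends partly on what happens after time zero; its wording also keeps people with no tests

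*Protocol*

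**What the plan says.** The rule stands in the Protocol under plans for addressing missing data. To limit bias from missing results, it removes "participants with only one full blood count, liver function test and renal function test in the first year of drug prescription in primary care". The same paragraph carries comparable steps over to CPRD Aurum.

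The time axis is set in the definition of the study population: "Cohort entry and start of follow-up: At first prescription and day 180 of the first primarycare prescription of a drug of interest respectively". The objectives describe a model conditional on "multiple prognostic factors available at six months of immune-suppressing drug prescription". The primary outcome runs "from 6 months of initial primary-care prescription to until 5-years after the initial prescription".

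The numbered exclusion list opens with "Exclusion criteria: Presence of any of the below prior to cohort entry". The blood-test rule is not in it.

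One route to the primary outcome requires "an abnormal blood-test result in the 15 days preceding or 45 days after the last prescription date", together with a prescription gap of at least 90 days. The other route is a clinical code. Incidence of discontinuation is to be reported for the entire period and separately for the "first 12-months of follow-up, and the subsequent period".

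**The concern.** A rule that decides who enters the analysis should use only what is known at time zero. Here the clock for the test count and the clock for follow-up both start at the first primary-care prescription, but the count runs on about six months after follow-up has begun. Two things that happen in that overlap affect inclusion:

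- **Time under observation.** Someone who dies, transfers or stops at day 220 has had less chance of a second test than someone who stays to day 365.
- **The outcome.** An event identified by an abnormal result adds at least one test to the count.

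At stake are the baseline hazard just after six months, which feeds every absolute risk prediction, and the incidence for the first 12 months of follow-up. If the rule is applied in both databases, the validation cohort is selected in the same way, and external validation would not expose the problem.

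Separately, *only one* does not literally include *none*. People with no tests can reach the outcome only through a code, so a rule meant to reduce missing-data bias keeps those with the most missing data.

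**Working it through.** **Overlap.** 365 − 180 = 185 days; 185/365 = 51% of the eligibility window lies inside follow-up. The first 12 months of follow-up are days 180-545, so 185 of those 365 days are also affected.

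**Cases under the two readings.**

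| Person | *Exactly one* excluded | *One or none* excluded |
|---|---|---|
| One test set by day 180, leaves day 220 untested | out | out |
| Same, but stays and is tested at day 300 | in | in |
| One set by day 180, abnormal test and stop at day 220 | in | in |
| No test by day 180, first test is the abnormal one, no repeat | out | out |
| No test at all, event by code only | in | out |
| No test at all, no event | in | out |

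The first two rows differ only in what happens after time zero. Rows three to five show that events are not uniformly favoured.

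**Size.** The protocol gives no figure for this rule, so only an illustration is possible. From the protocol: event rate 0.02 per person-year (sample-size section) and three-monthly testing (study background). The sample-size figure is not in dispute: 50/[(0.9 − 1) × ln(1 − 0.027/0.9)] = 16,415.4, so 16,416, with the 0.9 shrinkage target assumed. Further assumptions: everyone on drug at day 180; other exits 0.15 per year; testing independent of risk; Poisson tests averaging 2 or 4 a year with between-person gamma variance 0, 0.5 or 1; each event adds one test; 2,000,000 people per setting.

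Rates per 1,000 person-years in days 180-365 (percentages from unrounded rates):

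| Tests/yr | Variance | No exclusion | *Exactly one* out | *One or none* out |
|---|---|---|---|---|
| 2 | 0 | 20.11 | 20.92 (+4.0%) | 25.77 (+28.2%) |
| 2 | 0.5 | 20.03 | 17.74 (−11.4%) | 26.67 (+33.1%) |
| 2 | 1 | 19.91 | 15.24 (−23.5%) | 26.68 (+34.0%) |
| 4 | 0 | 19.89 | 20.20 (+1.5%) | 20.62 (+3.6%) |
| 4 | 0.5 | 20.05 | 19.48 (−2.9%) | 22.43 (+11.9%) |
| 4 | 1 | 19.96 | 17.79 (−10.9%) | 23.38 (+17.1%) |

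- Scheduled three-monthly tests with some missed visits, *one or none* out: about +2% to +8%, depending on how many visits are missed and how these are spread across people.
- Over follow-up to year 5: about 6% or less.
- If every event also brought a counted repeat test, the early rate would be 21.6-27.6 (*exactly one*) or 22.0-44.8 (*one or none*), and the five-year effect would rise too. The protocol does not say how much repeat testing to expect.
- Same rule, tests counted only in days 0-180: 19.7-20.3 under either reading, against a true 20.
- People with no test in the first year, kept by the literal wording: 2-20% of the cohort at 4 tests a year, 14-34% at 2 a year.

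**The case against.** The strongest reply is that this is a data-completeness filter and not a clinical eligibility rule. Its stated purpose makes *one or fewer* the natural reading, and the protocol's own testing frequency is three-monthly. With scheduled testing the early distortion is a few per cent, and the score concerns risk over five years, where it is smaller still. All of this stands as to size, and it is why the point is not graded higher. It does not remove the defect: a completeness filter still defines whose hazard is estimated, and no other section limits the count to day 180, sets a 12-month landmark, or deals with people who leave before day 365.

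A reader might infer that the rule always keeps events preferentially and so inflates early risk. The documents do not support that. Events may rest on a code with no numerical result, the abnormal test may be the person's first, and the qualifying test may fall before day 180 or after day 365. If 30% of events were code-only (an assumption), the inflation under *one or none* would fall from about 13% to 5% at 4 tests a year, and from 34% to 16% at 2 a year.

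Nor can the upper inflation figures and the zero-test complaint be pressed together. Those figures come from excluding *one or none*; the zero-test complaint requires *exactly one*, under which the rate can fall.

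A fair caution also applies to the remedy. Its unbiased result assumes that testing is unrelated to risk, whereas the study background says guidelines recommend closer monitoring of people with comorbidities. A day-180 rule can therefore still change the case mix, but it does so on information available at time zero.

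**Conclusion.** The concern holds as a design flaw that should be fixed before the cohorts are built. About half of the eligibility window lies after follow-up starts, and inclusion is tied to time under observation and to tests that enter the outcome definition.

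The direction and size of the bias cannot be determined from the protocol. With one test per event, the illustrations for days 180-365 span about −24% to +34%. The span depends on the reading of *only one* and on assumed testing frequency and spread. Under regular three-monthly testing with some missed visits and the *one or none* reading it is about +2% to +8%; to year 5 it is about 6% or less. Everything beyond the 0.02 rate and the three-monthly interval is assumed.

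The zero-test point is certain as a matter of wording. Whether the authors intended it is not known.

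**What to change.** 1. Count tests only from the first primary-care prescription to day 180, for example requiring at least one full blood count, one liver test and one renal test in that window.
2. State that no tests also fails the rule, and whether a shortfall in any one test type is enough to exclude.
3. Move the rule into the numbered exclusion list and say that it applies at day 180, in both databases.
4. Keep the first-year version as a sensitivity analysis, and report the number excluded under each.

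The edit is a sentence and a date in the code, but the threshold changes. Under the Poisson assumptions, requiring one test by day 180 excludes exp(−4 × 180/365) = 14% at 4 even tests a year, and 1/(1 + 2 × 180/365) = 50% at 2 uneven tests a year (variance 1). The first-year *one or none* rule excludes 2.1% + 8.0% = 10% and 33.5% + 22.5% = 56% in the same settings. Keeping a threshold of two by day 180 would cost much more: exp(−1.973) × (1 + 1.973) = 41% in the first setting. The threshold should be chosen before outcomes are seen, and the retained sample compared with the sample-size requirement for each drug.
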